#### Inclusion criteria

Specific inclusion criteria are as follows:

- Ethnicity: Hong Kong Chinese
- Age at enrolment: 8-13 years
- Spherical equivalent refraction (SER): -1.00 to -5.00 Dioptres (D)
- Astigmatism and anisometropia of 1.50 D or less
- Spectacle corrected monocular VA: 0.0 logMAR or better
- Free of ocular and systemic abnormalities might affect visual functions or refractive development
- Willingness to wear spectacle lenses regularly
- Parents' understanding and acceptance of random allocation of grouping

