#### 4.11 Statistical analysis

Data of two groups will be presented as the mean  $\pm$  SD. Only data of the right eyes will be used for data analysis if there are high correlation of data between two eyes. Baseline data between two groups between males and female will be analyzed by unpaired t-tests. Welch correction is applied if the difference of SD between the groups is statistically significant.

Primary outcomes

- Changes in auto-refraction (SER in diopters) with cycloplegia

Secondary outcomes

- Changes in axial length (mm) with cycloplegia

1. Repeated measures ANOVAs were used to compare the changes from the baseline visit in SER, and AL over time and between the two study groups in study. Interactions between time and groups were also assessed. If repeated measures ANOVA showed significant results between groups and significant interaction between time and groups, unpaired *t* tests were used to test for differences in SER, AL, between the two groups after the 24-month follow up period, and plots of the change will be plotted for showing trends. Bonferroni corrections were used to take account of *post-hoc* comparisons. The efficacy of myopic control will be determined by dividing the difference in mean SER changes of two groups with the mean SER change in the SV group times 100%.
2. The correlations between changes in Rx, biometric parameters and related factors (e.g. lens wear time, time spent on outdoor activities) are analyzed using Pearson correlations. Multivariate analyses of variance are used to examine the effect on treatment outcomes of various factors, including age, gender, initial refraction, etc.
3. To examine the choroidal response to MD in MS lens, changes in choroidal thickness over time and between two groups will be compared by the same statistically methods used for SER and AL mentioned above (*point 1*). Besides, the correlation between changes in choroidal thickness and axial length will be calculated using Pearson's correlation coefficient. Correlation between the pupil sizes, peripheral refraction and the effect in myopic control in terms of axial length elongation will be calculated using Pearson's correlation coefficient.

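### The lens effect and percentage efficacy are estimated without age or baseline values; adjusting gains precision at no cost in data if these explain more than about 2% of the variance in 2-year change

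*Combined protocol and SAP*

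**What the plan says.** Section 4.11, point 1, sets out three estimates of what the lens does:

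- For the course over time, "Repeated measures ANOVAs were used to compare the changes from the baseline visit in SER, and AL over time" and between the groups, with a group-by-time interaction.
- If the group effect and the interaction are both significant, unpaired t "tests were used to test for differences in SER, AL, between the two groups after the 24-month follow up period", with Bonferroni correction.
- Percentage efficacy, obtained by "dividing the difference in mean SER changes of two groups with the mean SER change in the SV group" and multiplying by 100.

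No covariate is named for any of them. Point 2 of the same section plans multivariate analyses of variance to examine the "effect on treatment outcomes of various factors, including age, gender, initial refraction" and further unnamed factors. It does not define a lens effect adjusted for those factors and does not name baseline AL.

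On reporting, the section says "Data of two groups will be presented as the mean" with its SD. It states no confidence interval for the lens effect or the efficacy. It also says "Baseline data between two groups between males and female will be analyzed by unpaired t-tests", without saying what follows if a difference appears.

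The candidate covariates are all available. Section 4.1 gives "Age at enrolment: 8-13 years" and a baseline SER range of -1.00 to -5.00 D. Sections 4.7 and 4.8.2 have refraction and AL measured at baseline. Section 4.5 specifies simple randomisation, so none of these is balanced by design.

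**The concern.** The children span five to six years of age and 4 D of starting myopia. If these characteristics predict how far a child progresses in two years, an analysis that ignores them leaves the predictable part in the error term. The lens effect on SER and AL, and the efficacy percentage derived from the SER changes, would then have wider uncertainty than the same data allow.

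Bias is not at stake. Under randomisation the unadjusted difference is valid, and power for the planned effect is already high at the expected number of completers. What can be gained is narrower intervals, mainly for the efficacy percentage. A secondary gain is that covariates fixed in advance remove any choice about adjusting after the baseline t-tests have been seen.

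**Working it through.** **Inputs from the plan.** Section 4.3: SD 0.6 D, difference 0.50 D, two-sided alpha 0.01, power 90%, 43 completers per group, dropout about 40%, 90 recruited per group. Section 4.1: mean progression about 1 D a year.

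**Assumptions.** R² is the within-group share of variance in 2-year change explained by the covariates; it is not in the documents and is shown from 0 to 30%. The SD of 0.6 D applies to 2-year change in both arms. Two covariates are used per outcome: age and that outcome's own baseline.

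**1. The plan's sample size.** n = 2 × (0.6/0.50)² × (2.576 + 1.282)² = 42.85, rounded up to 43, as stated. Then 43/0.6 gives 72. The t-based version gives 45, and 45/0.6 = 75, so the stated 72-75 also reproduces.

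**2. Unadjusted 24-month comparison.** Completers: 90 × 0.6 = 54 per arm.

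- SE = 0.6 × √(2/54) = 0.1155 D.
- 99% half-width (matching alpha 0.01) = 2.623 × 0.1155 = 0.303 D, on 106 degrees of freedom.
- Power by noncentral t = 95.4%.

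At 43 per arm, SE = 0.6 × √(2/43) = 0.1294 D and power is 88.7% (90.1% by the normal approximation).

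**3. Adjusted comparison.** With k covariates and N children analysed, the average SE, including the cost of estimating the slopes, is

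SE(adjusted) = SE(unadjusted) × √[(1 − R²) × (N − 3)/(N − k − 3)].

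For k = 2 the last factor is 105/103 at N = 108 and 83/81 at N = 86.

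| R² | SE ratio, 54/arm | SE (D) | 99% half-width (D) | Power | SE (D), 43/arm | Power, 43/arm |
|---|---|---|---|---|---|---|
| unadjusted | 1 | 0.1155 | 0.303 | 95.4% | 0.1294 | 88.7% |
| 0% | 1.010 | 0.1166 | 0.306 | 95.0% | 0.1310 | 87.8% |
| 2% | 1.000 | 0.1154 | 0.303 | 95.4% | 0.1297 | 88.5% |
| 5% | 0.984 | 0.1136 | 0.298 | 96.0% | 0.1277 | 89.6% |
| 10% | 0.958 | 0.1106 | 0.290 | 96.9% | 0.1243 | 91.4% |
| 20% | 0.903 | 0.1043 | 0.274 | 98.4% | 0.1172 | 94.6% |
| 30% | 0.845 | 0.0975 | 0.256 | 99.3% | 0.1096 | 97.1% |

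Break-even R² is 1 − 103/105 = 1.9% at 54 per arm and 1 − 81/83 = 2.4% at 43 per arm. In terms of children, 108/[(1 − R²) × 105/103] gives about 118, 132 and 151 at R² of 10, 20 and 30%, against 108 analysed.

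A simulation of 20,000 trials per R² (2, 5, 10, 20, 30%) at 54 per arm agreed: adjusted SE 0.1147, 0.1128, 0.1107, 0.1040 and 0.0976 D.

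**4. Percentage efficacy at 54 per arm.** Each arm mean has SE 0.6/√54 = 0.0816 D. By the delta method, SE(efficacy) = (0.0816/SV change) × √[1 + (MS change/SV change)²].

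- If SV children progress 2.0 D (1 D a year held constant for two years) and MS children 1.5 D, efficacy is 25% and its SE is 0.0408 × 1.25 = 5.10 points. The 95% half-width is 10.00 points unadjusted. Multiplying by the SE ratios above gives 10.00, 9.84, 9.58, 9.03 and 8.45 points at R² of 2, 5, 10, 20 and 30%.
- If SV children progress 1.5 D and MS children 1.0 D, efficacy is 33% and the 95% half-width goes from 12.82 points to 12.82, 12.62, 12.28, 11.58 and 10.83 points.

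In the first case the simulated SEs of adjusted efficacy were 5.19, 5.03, 4.90, 4.61 and 4.35 points, close to the formula's 5.10, 5.02, 4.89, 4.61 and 4.31.

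**5. Repeated measures ANOVA, and AL.** With complete data the between-group test in the ANOVA equals a t-test on each child's mean of the four changes, so the same SE ratios apply with R² taken for that mean. The documents give no between-visit correlation and no SD for AL, so absolute figures cannot be given for either.

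**The case against.** The strongest reply is that nothing here is wrong. An unadjusted analysis of a randomised comparison is legitimate, and the plan has power to spare. The 40% dropout is described as conservative. With 72 completers per arm unadjusted power is already 99.1%, and with 90 it is 99.8%. At 90 per arm an R² of 10% moves the SE only from 0.0894 to 0.0853 D. All of this stands, and it is why the point concerns precision only.

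Second, the documents do not show that R² is appreciable. Section 4.1 says progression at 8-13 years is fastest relative to other ages, which says nothing about variation within that band. No section says that baseline SER or AL predicts change. At R² of 5 to 10% the 99% half-width narrows by only 0.005 to 0.013 D. This also stands: the gain is conditional, and only the upper part of the range is notable.

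Third, analysing change from baseline already removes stable differences between children. That is true, but it fixes the coefficient of follow-up on baseline at 1 and does nothing about age. Any relation between change and baseline, or change and age, remains in the error.

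Fourth, point 2 might be read as an adjusted analysis. It studies the factors themselves. It does not say that lens group is in the model or that an adjusted effect will be reported, and its factor list is open-ended.

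Two limits on the figures should be kept in view. The power values are for the 24-month comparison alone and ignore the requirement that the ANOVA be significant first, as well as the Bonferroni correction. The break-even near 2% holds for two covariates per model; with all three in each model it is 3/105 = 2.9% at 108 children and 3/83 = 3.6% at 86.

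**Conclusion.** The point holds as an improvement in precision, not as a flaw in validity. The plan names no covariate for any of its three estimates of the lens effect, and point 2 does not supply an adjusted one.

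Adjustment pays once R² exceeds about 2%, and its worst case is negligible. The gain is modest at R² near 10% (SE about 4% smaller) and useful at 20 to 30% (10 to 16% smaller). Confidence in the size is only moderate, because R² is assumed throughout; the efficacy figures also assume 1.5 or 2.0 D of progression in the SV group. Stating confidence intervals for the lens effect and the efficacy is worthwhile whatever R² turns out to be.

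**What to change.** In Section 4.11, point 1:

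- Pre-specify age and baseline SER as covariates for the SER analysis, and age and baseline AL for the AL analysis, by ANCOVA at 24 months or a longitudinal model with the same covariates.
- State that these covariates are used whatever the baseline t-tests show.
- Compute the difference between lenses and the percentage efficacy from the adjusted means, each with a confidence interval.
- Report the unadjusted results alongside.

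The cost is a change of wording, with no added children, visits or measurements, and two degrees of freedom per model. If the covariates explained nothing, the SE at 54 per arm would be 0.1166 D instead of 0.1155 D and power 95.0% instead of 95.4%.

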### **4.3 Sample size estimation**

The number of subjects required for the clinical trial is based on the power calculation for subject numbers. We use 90% power to detect 0.50D difference (with 0.6D of standard deviation (SD)) in myopia progression between two groups with a significance alpha level of 0.01 (2-tailed); the minimum subject number required to complete the study in each group is 43. Assuming a conservative dropout rate of about 40%, 72-75 children are required in each group.

The project will recruit altogether 180 subjects: 90 for control group and 90 for experimental group.

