##### Secondary outcomes

- Changes in axial length (mm) with cycloplegia

Refraction and AL under cycloplegia will be measured at baseline and at six-month intervals for 2 years. One drop of proparacine 0.5% and then 1-2 drops of cyclopentolate HCL 1 % will be instilled to induce cycloplegia. Cycloplegic refraction will be measured by the open-field autorefractor (Shin-Nippon NVision-K 5001 autorefractor). Five measurements are obtained for each eye. The SER of the representative value from these 5 readings was used for statistical analysis. AL will be measured by IOL Master (Carl Zeiss) Five measurements will be taken and then averaged.

[figure not shown]
Myopia progression (change in refraction) over 2 years will be determined by the difference between SER (from cycloplegic autorefraction) at the fifth and the first (baseline) visits.

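### The 24-month comparison is tested only after two significant ANOVA results, and the 90% power in section 4.3 does not cover that sequence

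*Combined protocol and SAP*

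**What the plan says.** Section 4.7 lists the primary outcome as change in cycloplegic SER without a time point, but defines two-year progression as the "difference between SER (from cycloplegic autorefraction) at the fifth and the first (baseline) visits".

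Section 4.3 sizes the trial on a single difference in progression: "We use 90% power to detect 0.50D difference", with SD 0.6 D and two-sided alpha 0.01. It concludes that "the minimum subject number required to complete the study in each group is 43", then adds: "Assuming a conservative dropout rate of about 40%, 72-75 children are required in each group". Planned recruitment is 90 per group.

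Section 4.11, point 1, starts from the omnibus analysis: "Repeated measures ANOVAs were used to compare the changes from the baseline visit in SER", and likewise in AL, over time and between groups. The next step carries a condition: "If repeated measures ANOVA showed significant results between groups and significant interaction between time and groups". Only when both parts of it hold does the plan compare SER and AL at 24 months by t test. Bonferroni is applied to post-hoc comparisons, with no count of how many. The percent efficacy carries no condition: "The efficacy of myopic control will be determined by dividing the difference in mean SER changes of two groups", relative to the mean change in the SV group.

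Section 4.11 states no alpha for the ANOVA effects and does not say whether baseline enters as a level of time. No other section provides an ungated 24-month test.

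**The concern.** The contrast that matches the protocol's definition of two-year progression, and that the sample size is built on, is tested only if two other tests succeed first. Each asks a different question from the 24-month comparison.

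- The group effect averages over visits. A gap that builds towards 24 months is diluted.
- The time-by-group interaction, if the four follow-up changes are the levels, asks whether the gap changes between 6 and 24 months. A lens effect that appears early and is then held produces little or no interaction, however large it is at 24 months.

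A real 0.50 D difference at 24 months could therefore go formally untested under the plan's own rule. Whether that happens would depend on the shape of the trajectory and on two choices the plan leaves open: the gate alpha and the coding of baseline.

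**Working it through.** **Inputs from the documents.** Difference 0.50 D, SD 0.6 D, two-sided alpha 0.01, power 90%, 43 completers, dropout about 40%, 90 recruited per group (section 4.3). Follow-up at 6, 12, 18 and 24 months (section 4.2). Mean progression about 1 D a year (section 4.1).

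**Reproducing the plan's figure.** For two means, n = 2 × [SD × (z₀.₉₉₅ + z₀.₉₀) / difference]² = 2 × [0.6 × (2.576 + 1.282) / 0.50]² = 42.9, so 43 per group. Dropout: 43/0.6 = 71.7, so 72. Completers from 90: 90 × 0.6 = 54. The 43 follows from a plain two-group comparison; no visits, correlations or gate enter it. With the t distribution, the ungated power is 88.7% at 43, 95.4% at 54 and 99.8% at 90.

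**Direction.** The probability of three rejections cannot exceed the probability of the last one alone. The sequence therefore has at most these powers under any trajectory.

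**The trajectory that the protocol's figures suggest.** At 1 D a year, controls progress 2.0 D in two years. A 0.50 D gap is 0.50/2.0 = 25% slowing. If that slowing is even, the gaps are 0.125, 0.25, 0.375 and 0.50 D, with visit mean 1.25/4 = 0.3125 D.

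**One cell by hand** (43 per group, gate 0.01, compound symmetry with r = 0.7).

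- SD of a child's visit mean = 0.6 × √[(1 + 3 × 0.7)/4] = 0.528 D.
- Noncentrality of the group effect = 0.3125 / (0.528 × √(2/43)) = 2.74, against a critical value of 2.64 on 84 df. Power is 54.5%.
- Power of the interaction is about 78%.
- Under compound symmetry the two tests are independent: 0.545 × 0.783 = 0.427, against 0.429 by simulation.

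Here the group effect is the tighter limit.

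**Range by simulation.** The documents give no covariances, so five were assumed for the change scores, all with a 24-month SD of 0.6 D: compound symmetry (r = 0.7); a random walk without reading error; and a random walk, a random slope and an equal mix of the two, each with reading error SD 0.15 D. The interaction is Greenhouse-Geisser corrected, the 24-month test is at 0.01, data are complete, baseline is not a level, and no Bonferroni adjustment is made. Entries are the minimum and maximum over covariances.

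Linear gap, probability of passing the full sequence:

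| Completers per group | Gate 0.01 | Gate 0.05 | Ungated t test |
|---|---|---|---|
| 43 | 43-81% | 71-88% | 89% |
| 54 | 60-91% | 83-95% | 95% |
| 90 | 90% to over 99% | 97% to over 99% | over 99% |

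Without compound symmetry the ranges are 64-81% and 82-88% at 43, and 79-91% and 91-95% at 54.

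Earlier separation, same 0.50 D at 24 months:

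| Gap over time | Quantity | 43 completers, gate 0.01 | 54 completers, gate 0.05 |
|---|---|---|---|
| 0.25 D at 6 months, rising evenly to 0.50 D | full sequence | about 23-48% | about 65-78% |
| 0.25 D at 6 months, 0.50 D from 12 months | gate opens | 42-67% | 82-95% |
| 0.40 D at 6 months, then 0.50 D | gate opens | 4-7% | 17-23% |
| 0.50 D at every visit | gate opens | about 1% | about 5% |

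In the last row the interaction is truly null, so the gate opens at about its own alpha whatever the sample size.

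**Effect of coding baseline as a zero-change level.** The constant gap then passes the full sequence in 88-89% at 43. The linear gap gives 54-85% at 43 with a 0.01 gate, and 86-95% at 54 with a 0.05 gate.

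**The case against.** Section 4.11 can be read with the repeated measures ANOVA as the efficacy test and the t tests as follow-up. An omnibus test followed by pairwise tests is conventional, and the Bonferroni sentence refers to post-hoc comparisons. On that reading a closed gate costs one p-value: the group effect is ungated, and for a constant gap it has 96% to over 99% power at 43. This limits the consequence and stands. It does not rescue the 90%, because the visit-averaged group effect is not what section 4.3 powers either. For the linear gap at 43 and alpha 0.01 it has 54.5% under compound symmetry and 79-86% under the other covariances.

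The planned trial is also larger than 43. Falling to 43 from 90 would need 1 − 43/90 = 52% dropout, and the protocol already calls 40% conservative. At 54, with a 0.05 gate and a linear gap, the loss is small unless compound symmetry holds. Compound symmetry gives cumulative change the same spread at 6 months as at 24, which is hard to defend for progression. Both points stand for the linear case; neither covers a 0.01 gate or earlier separation.

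Finally, an early, complete gap sits badly with about 1 D a year. Controls would progress about 0.50 D by month 6, so a 0.50 D gap then means complete arrest followed by no further effect. The 1% and 5% figures are best read as the limiting case. Partial early separation is less extreme: 0.25 D at 6 months is 50% slowing at first, then 0.25/1.5 = 17% over the next 18 months. That path already loses a good deal.

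**Conclusion.** The concern holds. Section 4.11 conditions the 24-month test on two other significant results, and section 4.3 powers only the unconditional comparison. That the sequence has less power than the ungated test needs no assumption about trajectory.

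The size of the loss is not fixed by the documents. With 54 completers, against 95% ungated, the sequence gives 60-91% (gate 0.01) or 83-95% (gate 0.05) for a linear gap, and about 65-78% (gate 0.05) when half the gap is present at 6 months. A gap complete by 6 months leaves the test almost always unrun unless baseline is coded as a level. These figures rest on the assumed covariances, complete data, a 24-month test at the 0.01 of section 4.3, and no Bonferroni adjustment. Recruiting 90 per group absorbs much of the loss only for a linear gap with a 0.05 gate.

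What is at risk is the formal 24-month test, not all evidence of efficacy: the group effect, the group means and the percent efficacy do not depend on the gate. The rule should nevertheless be corrected, because as written it can leave a real two-year difference untested.

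**What to change.** In section 4.11, point 1:

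- Make the between-group difference in SER change at 24 months the primary test, by t test or as the 24-month contrast from the repeated measures model.
- Run it unconditionally at the two-sided 0.01 level of section 4.3, and report it with a confidence interval.
- Report the group effect, the time-by-group interaction and the trend plots as supportive, and state whether baseline is a level of time.
- Limit Bonferroni to any additional visit comparisons.
- Use the same ungated structure for AL as the secondary outcome.

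A single pre-specified contrast needs no gate to protect its type I error. The change brings sections 4.3, 4.7 and 4.11 into line. It is a change of wording only, with no new data and no additional children.

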#### **3.2 Aims of the study**

- To determine if wearing the MS lenses slows the progression of myopia and axial elongation in myopic schoolchildren over 2 years.
- To compare the changes in refractive error (Rx) and axial length (AL) in children wearing MS lens with those children wearing single vision (SV) spectacle lens (control).

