#### **4.4 Spectacle lenses**

##### MS lenses and spectacle prescription

The MS lens is a custom-made plastic spectacle lens. The lens power matches distant prescription. There are multi small defocusing zones of relatively positive embedded in the lens. Such design allows to introduce MD and to maintain clear vision simultaneously. The controls are the ordinary SV spectacle lenses are made of 1.6CR39HMC.

The final distance prescription of spectacles is determined on cycloplegic subjective refraction. The children will be instructed to wear lenses all the time.

*Treatment group: MS spectacle lenses*

*Control group: SV spectacle lenses*

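### The planned choroid–axial length correlation does not say how lens group is handled; taken over all children, a lens effect on both measures would by itself produce a correlation

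*Combined protocol and SAP*

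**What the plan says.** Section 4.11, point 3, plans two things for the choroid. The first is a group comparison: "To examine the choroidal response to MD in MS lens, changes in choroidal thickness over time and between two groups will be compared" by the methods used for refraction and axial length. The second, added to it, is a correlation: "the correlation between changes in choroidal thickness and axial length will be calculated using" Pearson's coefficient. No stratum, group term or analysis set is given for the correlation, and no other section supplies one.

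The only multivariable analysis is in point 2: "Multivariate analyses of variance are used to examine the effect on treatment outcomes of various factors, including age, gender, initial refraction, etc". Its named factors do not include lens group, and it does not deal with the choroid–axial length relation.

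A lens effect on axial length is what the trial sets out to show (section 3.2): "To determine if wearing the MS lenses slows the progression of myopia and axial elongation in myopic schoolchildren over 2 years". A lens effect on the choroid is tested in point 3 itself.

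Point 2 also correlates the changes with behaviour: "related factors (e.g. lens wear time, time spent on outdoor activities) are analyzed using Pearson correlations". It too is silent on lens group.

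**The concern.** A Pearson coefficient calculated over both groups combines two things: the association among children wearing the same lens, and the difference between the group means. If the lens moves both group means, the second part is not zero, and the coefficient departs from zero even if choroidal change says nothing about how much an individual eye grows. The stronger the lens effect on both measures, the larger this part becomes.

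The group comparisons already show whether each mean moved. The correlation adds information only if it reflects a relation that holds among children wearing the same lens. With the handling of group left open, a reader could take a coefficient that largely restates the two group differences as support for a mechanism. An analyst could also choose between pooled and within-group results after seeing both.

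**Working it through.** **The plan's own figure.** The documents give no figure for the correlation. The standardised effect borrowed below comes from section 4.3, so that calculation was checked first: difference 0.50 D, SD 0.6 D, two-sided alpha 0.01, power 90%.

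- Normal approximation: n = 2 × (2.576 + 1.282)² × (0.6/0.5)² ≈ 42.9, so 43 per group, as stated. The t-based version gives 44.5, so 45.
- Dropout of 40%: 43/0.6 = 71.7, so 72, and 45/0.6 = 75. This matches the stated 72–75.
- Recruitment is 90 per group, so 90 × 0.6 = 54 completers per group at the plan's dropout rate.

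**Inputs for the correlation**

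- Lens effect on axial length: d₁ = 0.50/0.60 = 0.833 within-group SDs. This is an assumption, because the documents give no effect size or SD for axial length and the refraction figure is borrowed.
- Lens effect on the choroid: d₂ is not given, so it is ranged from 0 to 1.0 SD.
- Association within each group: zero, by construction.
- Equal groups.

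**Size of the spurious correlation.** With two equal groups, the shift in means adds d₁d₂/4 to the covariance and d²/4 to each variance:

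|r| = (d₁d₂/4) / √[(1 + d₁²/4)(1 + d₂²/4)]

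For d₁ = 0.833, d₁²/4 = 0.174. Examples:

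- d₂ = 0.5: 0.104 / √(1.174 × 1.0625) = 0.093
- d₂ = 0.833: 0.174 / 1.174 = 0.148
- d₂ = 1.0: 0.208 / √(1.174 × 1.25) = 0.172

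**False-positive rate if the pooled coefficient is tested.** These come from 20,000 simulated trials per scenario, with normally distributed outcomes and no association within groups. The first two rate columns use 54 completers per group.

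| Choroid effect d₂ (SD) | Spurious \|r\| | 54 per group, alpha 0.05 | 54 per group, alpha 0.01 | 43 per group, alpha 0.05 | 90 per group, alpha 0.05 |
|---|---|---|---|---|---|
| 0 | 0.00 | 5% | 1% | 5% | 5% |
| 0.2 | 0.04 | 7% | 2% | 7% | 8% |
| 0.3 | 0.06 | 9% | 2% | 8% | 12% |
| 0.5 | 0.09 | 16% | 5% | 14% | 24% |
| 0.833 | 0.15 | 34% | 15% | 28% | 52% |
| 1.0 | 0.17 | 44% | 22% | 36% | 65% |

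The rate rises with sample size because the pooled coefficient estimates a quantity that is not zero.

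**After adjustment.** With the correlation taken given lens group, the mean r is about 0.00 and the false-positive rates are about 5% and 1% at the two alpha levels in every scenario.

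**The case against.** The strongest reply is that the plan does not say the groups will be pooled. It names the coefficient and not the children it is calculated on, and point 3 opens by referring to the response in the MS lens, which is compatible with analysis by group. This stands. A reader might infer that the plan prescribes a confounded analysis, but the documents support only that the handling of group is unspecified. The numbers above apply if the coefficient is taken over all children.

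Second, no significance test or decision rule is set for this coefficient, and the only alpha in the documents is the 0.01 used for the sample size. The false-positive rates are therefore conditional on someone testing it, and both alpha levels are shown. The coefficient itself stays modest: at |r| = 0.172 it accounts for under 3% of variance (0.172² = 0.030).

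Third, if choroidal change lies on the path from lens to axial length, conditioning on group removes the variation that the lens induces and answers a narrower question. That is fair, and it is a reason to let a labelled pooled value appear alongside. It is no reason to rely on the pooled value alone, which is non-zero whenever the lens moves both measures, whether or not they are linked.

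Fourth, one might infer that pooling also creates false wear-time correlations. The documents do not support this. The artefact needs wear time to differ by lens, and sections 4.4, 4.8.3 and 5.15 give every child the same instruction: "The children will be instructed to wear lenses all the time". If wear time is alike in the two groups, pooling creates no spurious correlation. At most it blends two relations that may differ between lenses.

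**Conclusion.** The point holds in a limited form. The plan leaves open how lens group enters the choroid–axial length correlation, and a coefficient over all children would mix the between-group shift with any association among children wearing the same lens. Under the stated assumptions the artefact ranges from nothing, if the lens affects only one measure, to |r| of about 0.17. The false-positive rate, if the coefficient is tested, ranges from nominal to several times nominal. Both ranges depend on an axial length effect borrowed from refraction and a choroid effect that the documents do not give.

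A reader might go further and conclude that the trial's evidence on efficacy or mechanism is undermined. The documents do not support that. The choroid is neither an aim nor a primary or secondary outcome, and the planned examination of choroidal response is the group comparison, with the correlation as an addition. The refraction and axial length comparisons and the sample size are untouched. This is a small improvement to a supporting analysis.

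**What to change.** In section 4.11, point 3, specify the choroid–axial length correlation as a partial correlation given lens group, or equivalently a regression of axial length change on choroidal change plus group. Report the coefficient within each group as well. If a pooled coefficient is also shown, label it as including the between-group difference.

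For wear time in point 2, it is enough to report the relation separately by lens group, so that the two are not blended.

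The cost is a sentence or two in the plan, a minor change to the analysis code and one degree of freedom for the adjusted correlation. No new data, visits or participants are needed.
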